#### Description of the study populations

HCPs:

HCPs will be described according to the data included in the HCP enrolment form. Tables and listings describing participating HCP characteristics will be produced (specialty, years in practice, geographic location, institution type, number of pregnant malaria (Registry) patients treated/site).

Patients:

Patients included in the study will be described according to demographic and background characteristics (e.g. age, ethnicity, duration and timing of exposure to Eurartesim™).

#### Pregnancy-related information

Frequency and type of pregnancy outcome will be stratified by the earliest trimester of exposure, demographics and medical background characteristics. Gestational weeks will be counted from the date of the last menstrual period, with the second trimester as beginning at week 14 and the third trimester as beginning at week 28. Women who discontinued the study prior to delivery will not be taken into account in the primary analysis. A sensitivity analysis of patients who did not complete the entire follow-up will be performed, in the same manner as described in the 'Primary analysis' section above.

Time-to-event variables will be analysed via survival analysis methods (e.g. Kaplan-Meier survival estimates and associated confidence intervals).

In order to control for potential confounders, pregnancy outcomes will be analysed according to parameters such as lifestyle factors, concomitant infections/diseases and medication use. Patient's Body Mass Index (BMI) will be calculated from the patient's height (cm) and weight (kg) data.

In order to optimize patient recruitment, patients with recurring malaria and Eurartesim™ use during pregnancy will be included in this pregnancy Registry in addition to first malaria infections. However, first and

	recurring malaria infections will be analyzed separately due to the					
	potential differences in disease aetiology and pregnancy outcomes.					
	Analytical methods					
	Continuous variables will be d	described by their mean, standard				
	deviation, median, quartiles 1 and 3, extreme values (minimum an					
	maximum) and the number of missing data.					
	Categorical variables will be described by the total and percentage of					
	each response method and the number of missing data.					
	Continuous variables will be compared using Student's t-test (2 groups)					
	or variance analysis (>2 groups)	. If the conditions for applying these				
	tests are not met (normality, h	omoscedasticity), the Mann-Whitney,				
	Wilcoxon (2 groups) or Kruskal-Wallis (>2 groups) non-parametric tests will be used.					
	Categorical variables will be compared between subgroups using the					
	Chi-2 test if the theoretical total of each class studied is greater than 5.					
	Otherwise Fisher's exact test will be used.					
	The ordinal variables will be compared between subgroups using a					
	Cochran-Mantel-Haenszel test.					
	Hypothesis formulation will be bilateral. The tests will be performed fo					
	first species alpha risk of 5%.					
Registry timelines	These timelines are based on I	Eurartesim™ being available on the				
	market by June 2012:					
	Validation of study documents:	June 2012				
	Ethics submission:	June 2012				
	Launch of Eurartesim ™ :	June 2012				
	First patient in:	July2012				
	Recruitment rate analyses:	December 2012, every 1 year after				
	Interim statistical analyses:	June 2014, every 2 years after				
	Last patient in:	May 2017				
	Final Clinical Study Report:	September 2019				

## 3. Introduction and justification for the study

Currently, malaria is one of the leading killer diseases in the world. According to the newly released WHO Malaria Report 2008, "there were an estimated 247 million malaria cases among 3.3 billion people at risk in 2006 causing nearly a million deaths, mostly of children under 5 years. One hundred and nine countries were endemic for malaria in 2008, 45 within the African region".

Eurartesim™ (dihydroartemisinin (DHA) - piperaquine (PQP)) is an artemisinin-based combination therapy (ACT), which involves the simultaneous use of two or more blood schizontocidal medicines with independent modes of action and, thus, different biochemical targets in the parasite. The rationale is two-fold: i) the combination is often more effective; and ii) in the very rare event that a mutant parasite resistant to one of the medicines arises de novo during the course of the infection, this resistant parasite will be killed by the other antimalarial medicine. This mutual protection is thought to prevent or to delay the emergence of resistance and ACTs have replaced chloroquine in treating malaria because malaria parasites have become resistant to the old malaria drugs. To realize the two advantages, the partner medicines in a combination must independently be sufficiently efficacious in treating malaria (WHO, 2010).

The ACTs have undergone the three trial stages and pre-clinical data has demonstrated embryotoxicity (lethality and teratogenicity) with artemisinin compounds. Substantial data are available in patients for DHA-PQP combination treatment, including neurotoxicity of artemisinin derivatives, cardiotoxicity and QTc prolongation, and reproductive toxicity (i.e. DHA embryolethality in animals). Previous animal models have established that artemisinin derivatives, as well as DHA, have serious embryotoxigenicity in rat and rabbit embryos/foetuses (Sigma-Tau, 2009).

To date, some recent *in vitro* results on DHA studied in the rat whole embryo culture demonstrated that DHA primarily affected primitive red blood cells (Longo *et al*, 2006a; Longo *et al*, 2006b). Tissue damage and effects on embryo morphology were attributed to this. Despite the absence of maternal anaemia, yolk sac haematopoiesis was also seen as the target of DHA *in vivo*. Resulting anaemia leads to cell damage, which, depending on its degree, can be either diffuse or focal. Embryo response to acute anaemia varies from complete recovery to malformation and death depending on the degree of cell death induced.

*In vivo* studies (White *et al*, 2006) showed that four artemisinins (artesunate, DHA, artemether and arteether) administered orally to pregnant rats on day 10 post-coitum

caused nearly equivalent effects in terms of embryolethality and teratogenicity (cardiovascular defects and shortened and/or bent long bones). This, therefore, suggests that embryotoxicity is an artemisinin class effect (WHO, 2006). The developmental toxicity is thought to be dependent on the high sensitivity of embryonic erythroblasts to artemisinins compared to adult erythroblasts. Since decreases in reticulocyte count occur at therapeutic doses in humans following artemisinin treatment, there is concern that this could be accompanied by marked decreases in embryonic erythroblasts and developmental toxicity if artemisinin is administered during the first trimester of pregnancy. DHA affects human erythropoiesis *in vitro*, in a dose- and time-dependent manner; the target populations seem to be the pro-erythroblasts and basophilic erythroblasts, suggesting that DHA toxicity is limited to primitive human erythropoiesis.

In a further study, Rijken *et al* (2008) treated 50 pregnant women with recurrent Plasmodium falciparum infections (despite 7 day treatments with quinine or artesunate (+/- clindamycin) or both) with DHA-PQP. The gestational age at DHA-PQP treatment was 23.7±8.2 (9.2–39.1) weeks. 45 of the women had a known pregnancy outcome. Two infants were reported to be abnormal at birth; one with a small umbilical hernia (exposed to treatment at 24 weeks) and one diagnosed clinically with Patau syndrome (trisomy 13) (exposed to treatment at 34 weeks), who subsequently died at 6 hours of age. The remaining infants were all observed at 1 month of age and found to be healthy. The two abnormalities identified in the newborns are unlikely to be drug related. Thus, DHA-PQP was effective and well tolerated and there was no evidence of toxicity for the mothers or the newborns.

The phase four trial, or post-marketing phase, where the drugs are already in use on the markets, seeks to examine the risks and benefits of the new drug in different and larger segments of the population. This phase is important because it examines issues such as the longer-term effects of drug exposure on larger populations. Post-marketing surveillance is also important because even the most well designed phase three studies might not uncover every problem that could become apparent once a product is widely used. Furthermore, the new product might be more widely used by groups that might not have been well studied in the clinical trials and there might be reports of adverse drug reactions once a drug becomes available on the open market (African Media and Malaria Research Network, 2010).

This epidemiologic surveillance registry is necessary because of the potential for exposure in the first trimester of pregnancy and the unknown risks in pregnancy for any new chemical entity. The current lack of data regarding Eurartesim™ use during pregnancy makes such a registry an essential component of the ongoing assessment of

the safety of Eurartesim™. Through the registry, patients exposed to any formulation of Eurartesim™ during pregnancy will be registered by healthcare providers (HCPs), the pregnancies followed and the outcomes ascertained through follow-up. This information will be used to detect any potential risks to pregnant women and/or teratogenic effects in pregnancies exposed to any formulation of Eurartesim™.

This study is required in response to questions from the European Medicines Agency (EMA), to ensure that data regarding Eurartesim™ use for the treatment of malaria whilst pregnant are collected on missing populations, e.g. Caucasians.

This protocol details strategy considerations and assessment of study feasibility for a pregnancy Registry in Europe for patients exposed to Eurartesim™ whilst pregnant. The proposed pregnancy Registry is important in fulfilling the EMA post-marketing requirements.

## 4. Study objectives

- The primary objective of this study is to assess the live birth incidence of minor and major congenital birth defects following exposure to Eurartesim™ for the treatment of malaria whilst pregnant or in the one (1) month (30 days) prior to conception.
- The secondary objective of this study is to assess maternal, fetal and infant outcomes following exposure to Eurartesim™ for the treatment of malaria whilst pregnant or in the one (1) month (30 days) prior to conception.

## 5. Methodology

## 5.1 Study Design

A European multi-centre pregnancy Registry for patients exposed to Eurartesim™ for the treatment of malaria whilst pregnant will be compiled, incorporating Belgium, France, Germany, Italy, The Netherlands, Spain and the UK. HCPs will include all patients meeting the inclusion criteria and agreeing to take part in the Registry.

Diagnosis of malaria will be clinically and parasitologically confirmed.

Protocol N° 3351 CONFIDENTIAL

#### 26/06/2012 Version - 12.0

#### **TABLE 1: STUDY FLOW CHART**

Assessment by HCPs	Visit 1 (Enrolment)	Visit 2 (4 weeks post- enrolment)	Visit 3 (4 weeks prior to expected due date)	Visit 4 (end of pregnancy)	Visit 5 (6 weeks after end of pregnancy)	Visit 6 (14 weeks after end of pregnancy)	Visit 7 (12 months after end of pregnancy)
Date of the visit	x	x	x	x	x	x	x
Socio-demographic characteristics	x *						
Lifestyle data	x						
Malaria history	x						
Date of exposure to Eurartesim ™	x						
Pregnancy data and obstetrical history	x						
Maternal complications	x	x	x	x	x	x	
Fetal complications	x	x	x	x			
Concomitant medication use	x *	x	x	x			
Significant medical history	x*						
Exacerbation of pre-existent clinical condition		x	x	x			
Comorbidities		x	x	x			
AEs/SAEs		x	x	x	x	x	X
Maternal mortality				x	x	x	
Infant mortality				x	x	x	
Infant development					x	x	X

\*These data will also be collected for the biological father.

## 5.2 Selection criteria

#### Inclusion Criteria:

The following patients will be included in the study:

- Women;
  - who have received Eurartesim™ for malaria whilst pregnant, within one (1) month (30 days) before or at any time after conception, or
  - whose partner (the biological father) has received any formulation of Eurartesim™ for malaria within one (1) month (30 days) prior to conception (Committee for Medicinal Products for Human Use, 2005), and
  - who have been informed and agree to participate in this study.

#### **Exclusion Criteria:**

The following patients must not be included in the study:

- Women who refuse to participate.
- Women participating in a clinical trial at the time of inclusion in this study.

## 5.3 Health Care Providers (HCP) Selection Criteria

HCPs known to treat and follow-up malaria patients will be invited to collaborate in this Registry. Women who are not part of one of the selected sites will be able to contact their HCP who will contact Sigma-Tau on their behalf in order to be included in the Registry. In addition, all patients with pregnancies reported to the company as spontaneous events by HCPs will also be asked to participate in the pregnancy Registry. All spontaneous events (e.g. pregnancy exposure, birth defects) will be reported, regardless of the country they are coming from.

An invitation letter will be sent out with a summary of the study and a reply form to identify HCPs in each country. Non-respondent HCPs will be contacted by telephone by Epidemiologic Research Associates (ERAs) trained for this study, to determine the status regarding their participating.

The reply form and qualification telephone call will enable the collection of information about the sites (e.g. speciality, type of institution/practice, number of patients seen, reasons for refusal) and the assessment of their ability and willingness to participate.

#### 5.3.1 Educational Outreach Program

An educational 'outreach program' will be implemented to increase awareness of the Registry among both patients and Health Care Providers (HCPs), and increase both patient and HCP participation.

The awareness campaign will include the following elements in each country initiated into the study:

- Patient Information Sheet included with product packaging (including contact data for each country).
- Targeted educational material.
- Registry website and web awareness activities, including internet based recruitment.
- Advertising and scientific presentations at specifically targeted meetings such as the tropical medicine society meetings, etc.
- Partnering with interested organisations.

Educational material, targeting those in traveller's medicine and infectious disease, will inform HCPs of the Registry and provide information on how they can refer patients for inclusion and participation.

A Registry website will provide information regarding the Registry, targeted at both patients and HCPs, and will describe the process for participation for both patients and HCPs, including relevant contact details; this website will be designed with a section for patients and a section for HCPs.

Internet based recruitment, using keyword searches, will also be employed. When an internet user uses a search engine, relevant keywords (e.g. malaria, EurartesimTM) will be rerouted to the Registry website, thus, raising awareness of the Registry and providing a means of both patient and HCP participation.

Additional web awareness activities will include placing advertisements and links on relevant sites (i.e. Medicines for Malaria Venture [MMV]).

There will also be advertising at annual professional society meetings (such as the European Society of Clinical Microbiology and Infectious Diseases) to increase HCP awareness and encourage referral of appropriate patients.

Page 22 of 56

In addition, the Sponsor will contact these organisations in an effort to increase awareness of the Registry to the public and HCPs:

- European Network of Teratogen Information Services (ENTIS)
- European Surveillance Network of Congenital Anomalies (EUROCAT)
- European Collaboration of Craniofacial Anomalies (EUROCRAN)
- International Clearinghouse for Birth Defects Monitoring Systems

A review of literature will be performed routinely to ensure that HCPs publishing any relevant maternal exposure are contacted for inclusion in the Registry.

## 5.4 Sample Size Calculation

Data for this pregnancy Registry will be regularly collected until the sample size required to detect a 2-fold or greater increase relative to the expected background rate of all birth defects and spontaneous abortions is reached. This will provide an adequate sample to ensure understanding of maternal drug safety. The Registry will be closed to new entries once this number of women with validated follow-up information has been reached and in agreement with the EMA; the data will be transferred to another independent Registry, if in acceptance with the other Registry, and according to ethical standards and national legislation at that point in time. These data will then be compared to background rates to see if there has been a significant increase in birth defects or pregnancy loss amongst these patients. A sensitivity analysis will be performed on the data to check other contributing factors.

The following sample size is derived to detect a clinically significant difference (i.e. a >2x increase in the outcome of concern) relative to expected background rates. In Europe, the assumed background risk of all reported birth defects is 23.719 per 1,000 births (EUROCAT, 2009) and the background rate of spontaneous abortion is 85.6 per 1,000 (Tata *et al*, 2005). Thus, assuming 80% power, 0.05 significance level (one-sided) and a loss to follow-up rate of 5%, we would require 376 pregnant women exposed to EurartesimTM in order to be able to detect a 2-fold or greater increase in birth defects and a 1.5-fold or greater incidence in spontaneous abortions with a one-group test. Calculations are based on a normal approximation to a Binomial distribution (equivalent to a chi-square test). Employing a 5% loss to follow-up rate is deemed appropriate as

utilising the services of ProClinica (refer to Section 7.3) to actively follow-up patients via direct patient contact should reduce the degree of loss to follow-up in this Registry.

The method of site allocation was based on the weight according to reported malaria case-load per country (European Centre for Disease Prevention and Control, 2010) combined with the findings of the feasibility study (refer to Appendix 1). We would, therefore, require a total of 57 sites, represented across Belgium, France, Germany, Italy, The Netherlands, Spain and the UK, in order to recruit 376 patients over 5 years. For Belgium, Italy, The Netherlands and the UK, where data was currently unavailable for the feasibility study, the most conservative estimates were extrapolated from the other countries' responses. The Belgium site queried in this feasibility study did not report any recent cases of malaria among pregnant women. However, based on European Centre for Disease Prevention and Control malaria statistics (European Centre for Disease Prevention and Control, 2010), Belgium has a high reporting rate of malaria per persons among EU countries, so it has been included in the protocol to ensure adequate enrolment of pregnant women into the Registry.

Analyses and data on current recruitment rates will be provided on an annual basis. If analyses show that recruitment rates are lower than anticipated/required, attempts will be made to further increase the number of study sites, e.g. by including further countries.

## 5.5 Data collected

Patient's identities will remain confidential and a Patient ID number will be assigned for the purpose of communicating with the reporting HCP. Eligible patients will be asked to give signed, witnessed informed consent for the confidential release of data. The biological father will also be requested to give consent for the release of data referring to him; if the mother consents to participate in the registry but the biological father doesn't, then the mother and her infant will still be included in the registry but no data will be collected on the biological father.

In addition to data collected by HCPs during visits and in order to minimize lost-to-follow up rates, a supplementary system of active patient follow-up will be undertaken by a dedicated and independent unit, so called ProClinica (refer to Section 7.3), which is specialised in direct and proactive patient management in studies. This independence will ensure confidentiality and safekeeping of the collected data. At study initiation, enrolling HCPs will ask patients to consent through a Contact Order Form to allow ongoing contact by ProClinica, if needed. The patients will be asked to provide their contact details, contact details of a relative and of their usual referral HCP and authorization to contact the relative then the referral HCP following an escalated contact process.

The non-reception of the iterative information from HCPs through the CRF completion in due time as scheduled in the protocol will trigger ProClinica intervention.

Triggering for this intervention will be:

- No information received from the HCP 3 months after patient enrolment
- No information received from the HCP 3 months after expected date of delivery
- No information received from the HCP 3 months after expected date of delivery + 12 months

Several attempts to contact the patient by telephone, then a relative, then the referral HCP will be performed (3 attempts for each type of contact). In case these telephone contacts are unsuccessful, a short questionnaire will be sent by mail to the patient. This process will be performed up to 3 times (according to the 3 triggering events).

The main objective of these contacts will be to remind the patient of the importance to comply with the Registry assessment schedule, to detect and document the reasons for non-collection of information (i.e. serious safety event, withdrawal from the study, personal reason).

A structured short screening of pregnancy outcome, easy to understand by patients, will be performed and documented. A copy of the completed screening questionnaire will be systematically sent to the concerned Registry HCP. Should the screening detect an abnormal pregnancy outcome and/or a serious safety event on the child, the concerned Registry HCP will be asked to follow up and medically confirm the event. If the concerned Registry HCP is not able manage this medical confirmation, ProClinica will seek to get a medical confirmation through patient treating HCPs.

All actions performed by ProClinica and information collected will be documented.

Patients will be considered lost to follow-up if a patient's expected delivery date has passed and outcome data have not been entered into the Registry within one year following the expected delivery date, and all attempts for contact failed. Reasons of loss to follow-up (e.g. patient not contactable, moved away, died) will be documented.

The following data will be collected from the HCP:

Occupation categories will be defined as recommended by EUROCAT (EUROCAT, 2009).

#### **HCP enrolment form:**

- Specialty.
- Years in practice.
- Geographic location.
- Institution type.
- Number of pregnant malaria patients currently treating.

#### At enrolment visit:

- Date of the visit.
- Socio-demographic characteristics of the mother (ethnicity [based on the standard definitions of ethnicity used in the EU country where the woman is enrolled in the Registry], country of birth, primary language and socio-economic status [based on current or most recent occupation and years of formal education]).
- Socio-demographic characteristics of the biological father (age and current or most recent occupation).
- Mother's lifestyle data (height [cm] and weight [kg], radiation exposure, smoking status [never/past/current], alcohol consumption [weekly units], recreational drug use.
- Mother's malaria history (date of malaria diagnosis, date of most recent Eurartesim™ administration and dose, previous Eurartesim™ administrations, other treatment taken for malaria).
- Pregnancy data (date the pregnancy was registered).
- Estimated date of delivery/date of last menstrual period.
- Previous or concurrent maternal complications.
- Health status of the fetus, if it is already known at time of enrolment, i.e. via ultrasound.
- Pregnancy outcome, if already known at time of enrolment.

- Obstetrical history (number of previous pregnancies and outcome).
- Significant medical history of the mother and the biological father.
- Concomitant medication use in the mother and the biological father in the one (1) month (30 days) prior to conception.

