#### 4-weeks post-enrolment and 4-weeks prior to expected due date:

- Date of the visit.
- Serious adverse events (drug related or not) in the mother since previous visit/contact.
- Exacerbation of pre-existent clinical condition in the mother since previous visit/contact.
- Comorbidities in the mother since previous visit/contact.
- Concomitant medication use in the mother since previous visit/contact.
- Maternal complications since previous visit/contact.
- Fetal complications since previous visit/contact; any spontaneous abortions (≤28 weeks gestation), elective abortions, ectopic pregnancies, late fetal or neonatal deaths (>20 weeks gestation), premature deliveries (≤37 completed weeks).

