#### Description of the study populations

- HCPs:

HCPs will be described according to the data included in the HCP enrolment form. Tables and listings describing participating HCP characteristics will be produced (specialty, years in practice, geographic location, institution type, number of pregnant malaria (Registry) patients treated/site).

- Patients:

Patients included in the study will be described according to demographic and background characteristics (e.g. age, ethnicity, duration and timing of exposure to EurartesimT).

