#### Pregnancy-related information

Frequency and type of pregnancy outcome will be stratified by the earliest trimester of exposure, demographics and medical background characteristics. Gestational weeks will be counted from the date of the last menstrual period, with the second trimester as beginning at week 14 and the third trimester as beginning at week 28. Women who discontinued the study prior to delivery will not be taken into account in the primary analysis. A sensitivity analysis of patients who did not complete the entire follow-up will be performed for the main study outcomes, in the same manner as described above in the 'Primary analysis' section.

Time-to-event variables will be analysed via survival analysis methods (e.g. Kaplan-Meier survival estimates and associated confidence intervals).

In order to control for potential confounders, pregnancy outcomes will be analysed according to parameters such as lifestyle factors, concomitant infections/diseases and medication use. Patient's Body Mass Index (BMI) will be calculated from the patient's height (cm) and weight (kg) data, using the following equation:

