## 6.3 Confounding bias

Concomitant infections/diseases and medication use may have a potential confounding influence upon the pregnancy outcome and maternal complications. In order to control for potential confounders, details of any concomitant infections/diseases and medication use will be collected and pregnancy outcomes will be analysed according to these parameters.

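### As listed, the enrolment data never ask for the mother's non-malaria medication between conception and enrolment, and her age is not a listed item

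*Protocol*

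**What the plan says.** **Medication windows.** Protocol Section 5.5, under the enrolment visit, asks for "Concomitant medication use in the mother and the biological father in the one (1) month (30 days) prior to conception". The Summary (Section 2) repeats this item. At 4 weeks after enrolment and 4 weeks before the due date the item becomes "Concomitant medication use in the mother since previous visit/contact", and the end-of-pregnancy list uses the same window. Table 1 ticks concomitant medication at Visit 1 but states no period. Antimalarials are handled separately: the malaria history at enrolment covers Eurartesim administrations and other malaria treatment.

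**Use of these data.** Section 5.7 (Primary analysis) describes birth defects and spontaneous abortion by factors that include medication use. Section 6.3 says that "details of any concomitant infections/diseases and medication use will be collected and pregnancy outcomes will be analysed according to these parameters".

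**Age.** The mother's socio-demographic items are ethnicity plus "country of birth, primary language and socio-economic status [based on current or most recent occupation and years of formal education". Age is not among them. The father's list does have it: "Socio-demographic characteristics of the biological father (age and current or most recent occupation". Section 5.7 nevertheless states that "Patients included in the study will be described according to demographic and background characteristics (e.g. age, ethnicity, duration and timing of exposure" will be used, and that "Frequency and type of pregnancy outcome will be stratified by the earliest trimester of exposure, demographics and medical background characteristics". Sections 6.1 and 7.2 collect age for eligible women who are not included, and Section 6.1 does so in order to compare them with included women.

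**The concern.** The enrolment item looks back from conception, and the first follow-up item looks back only to enrolment. Between the two lies the part of pregnancy already past when the woman joins. Section 3 justifies the registry by possible first-trimester exposure and describes the embryotoxicity concern in that period, so the blank includes the weeks of greatest interest.

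The registry has no concurrent comparator. Incidences are set against external background rates. If a defect or loss followed another drug taken in early pregnancy, it would count in the registry incidence, and the planned breakdown by medication use could not show that the other drug had been present. A statistical analysis plan cannot repair this, because it cannot analyse data that were not collected.

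The missing age item is simpler. The planned description, the stratification by demographics and the comparison with non-included women all need a variable that the list for included women does not contain.

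**Working it through.** The plan states no figure on this point, so there is nothing to reproduce. The check sets the collection windows against the timeline of a pregnancy.

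**Step 1: coverage of non-malaria maternal medication (Section 5.5)**

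| Period | Item that covers it |
|---|---|
| 30 days before conception | Enrolment item |
| Conception to enrolment | None |
| Enrolment to Visit 2 | Visit 2, since previous contact |
| Visit 2 to Visit 3 | Visit 3, since previous contact |
| Visit 3 to end of pregnancy | Visit 4, since previous contact |

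Table 1 does not fill the second row, because its tick at Visit 1 carries no window.

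**Step 2: length of the gap**

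Inputs:
- Weeks are counted from the last menstrual period and the second trimester begins at week 14 (Section 5.7, Pregnancy-related information).
- Conception at week 2 is an assumption.
- The enrolment weeks below are illustrative. The protocol gives no expected distribution.

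Formulas, with *w* the week of enrolment:
- Unrecorded weeks = *w* − 2.
- Share of the post-conception first trimester unrecorded = (min(*w*, 14) − 2) / (14 − 2).

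| Enrolment week | Unrecorded weeks | Share of first trimester after conception |
|---|---|---|
| 6 | 6 − 2 = 4 | 4/12 = 33% |
| 10 | 10 − 2 = 8 | 8/12 = 67% |
| 14 | 14 − 2 = 12 | 12/12 = 100% |
| 20 | 20 − 2 = 18 | 12/12 = 100% |
| 40 (outcome known at term) | 40 − 2 = 38 | 12/12 = 100% |

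The last row is a case that the protocol allows. The enrolment list includes the pregnancy outcome where it is already known, and Section 6.1 keeps women with known fetal status eligible while conceding that those with a poor outcome may be more inclined to enrol. Read literally, the lists ask such a woman for no non-malaria medication taken during the pregnancy.

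**Step 3: age**

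Age is listed for the father (5.5) and for non-included women (6.1, 7.2), but not for included women (5.5). It is required for included women by the patient description (5.7) and by the comparison in 6.1, and it falls naturally under the demographics used for stratification (5.7).

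**The case against.** The best reply is that this is loose drafting and not a decision to leave pregnancy blank. Section 6.3 promises details of any concomitant medication, Table 1 ticks medication at Visit 1 without limiting the period, and the plan to describe patients by age shows an intent to record it. The CRF is not shown and may ask for both. This stands as to intent. It does not close the gap: Section 7.4 says that the CRF is still to be developed, so the Section 5.5 lists are its specification, and a CRF that follows them reproduces the omission.

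Four stronger readings are tempting, and the documents do not support them.

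- **That confounder control fails altogether, or rests on medication alone.** Section 5.7 also names concomitant diseases, lifestyle factors, demographics and medical background. Section 5.5 collects smoking, alcohol, recreational drugs, radiation, and obstetrical and medical history. Medication before conception and after enrolment is recorded, and long-term drugs may appear there. The primary estimate is an incidence with a 95% confidence interval, and the gap does not change it. What suffers is the interpretation.
- **That no early co-medication at all is recorded.** Antimalarials are captured through the malaria history.
- **That the gap can be sized from the earlier series of 50 women in Section 3, treated at 23.7±8.2 weeks.** Those women had recurrent infection after other treatment, and treatment timing there is not enrolment timing in a European registry that takes first and recurrent infections. Most of them were also treated after the first trimester, whereas misattribution of an early defect matters most for women exposed in it. Section 5.7 stratifies outcomes by earliest trimester of exposure.
- **That all events before enrolment are missed because Table 1 starts AEs/SAEs at Visit 2.** Maternal and fetal complications are ticked at Visit 1, and fetal status and any known outcome are recorded then. Section 7.3 calls for all AEs and SAEs up to 12 months after delivery and does not set the start at Visit 2.

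**Conclusion.** The point holds in a limited form. As written, the protocol does not request non-malaria maternal medication from conception to enrolment. This undermines the planned description of birth defects and spontaneous abortion by medication use in the window that the registry exists to examine. The loss runs from about a third of the post-conception first trimester (enrolment at week 6) to all of it (week 14 or later), and to the whole pregnancy for a woman enrolled after it has ended. These figures rest on conception at week 2 and on assumed enrolment weeks. The real distribution is unknown, so no single overall figure can be given.

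Maternal age is a plain omission from the list. Age is a named descriptor, not a named confounder, so the claim is only that planned analyses call for a variable that the enrolment items do not supply. Both gaps should be closed before the first patient is enrolled, since information not requested at enrolment becomes harder to recover later.

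**What to change.** In Section 5.5 and the Summary, reword the mother's enrolment medication item to run from 30 days before conception up to enrolment, or to the end of pregnancy if that came first, with start and stop dates. Split off the father's item and leave his window unchanged. State the same window in Table 1 at Visit 1.

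Add maternal age or date of birth to the enrolment socio-demographic items, and carry it into the demographic tables and the comparison with non-included women.

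The cost is one changed item and one added field at an existing visit, with no effect on sample size. The downside is a longer recall period for the mother, which is greatest for women who enrol late.
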